### **Phase 3: Process evaluation**

This phase aims to collect feedbacks from online focus group interview to explore the barriers and facilitating factors in implementing the intervention, figure out additional problems which may affect the intervention, and refine the study design for a future full power RCT.

### **Ethical issues and data safety**

Ethical approval has been obtained from the Research Ethics Committee of The Hong Kong Polytechnic University (HSEARS20220127002) and the Research Ethics Committee of Xiang Ya Hospital of Central South University (KE202203129) to conduct this study. All participants will be reminded of the voluntary nature of the research and will be provided a participant information sheet. All information of participants will be kept confidential, and the information will be destroyed three years after the whole research. Participants can withdraw during any period in this research without any penalty or influence in their clinical rotation. There will be a clear written and verbal explanation of this study to all participants. The protocol will be prospectively registered at ClinicalTrials.gov. All participants will be asked to sign a written consent before this study starts.

### **Data Collection**

The interview guide for focus group interview will include a series of open-ended questions. The interview guide will be used to interview one participant before an official interview (phase 1 and 3). All focus groups' discussions will be recorded with videotaping online and transcribed verbatim. A detailed field note will be used to record the participants' non-verbal expressions, and emotional status of the informant and reflective notes will be used to record the researcher's speculation, feelings, and impressions towards the participants in the interview. Wen Juan Xing, an online

---

platform will be used to administer the self-assessment questionnaires. Only the researcher (the Ph.D. student) who has the password can login into this platform and access the data. The data will be kept in a U Disk Encryption that could only be accessed by the Ph.D. student with the password or others who is authorized. Tencent Video Conference will be used to conduct online intervention. All participants will receive a password and one-time access link to login the Tencent Video Conference. All participants' voices and facial expressions can be wholly captured. Each interview which lasts about 60 minutes will be recorded by videotape.

### **Data Management**

Information on the scales will be collected, coded, and enter SPSS 26.0 software to establish a database. A research assistant will help data entry. The PhD student and the research assistant will double-check the dataset of the raw data to make sure the data is accurate. Data will be kept strictly confidential. All participants will be anonymous in this study with only a code to represent his or her identity. Personal particulars will be removed in the analysis, all electronic files will be kept in a U Disk Encryption that could only be accessed by the PhD student with the password or others who is authorized.

### **Data Analysis**

#### **Quantitative data analysis**

The demographic characteristics of participants will be presented by using descriptive statistics; means, standard deviation (SD), or percentage, if appropriate. The demographical variables and outcome variables were compared between groups at baseline. Numerical variables will be analyzed by an independent t-test, and nominal variables will be analyzed by  $\chi^2$ . Supposing the data cannot satisfy the requirement of parametric analyses, the Mann-Whitney U tests will be performed to compare the scores obtained from the four Scale among intervention and control groups created according to demographic characteristics. Generalized estimated equations (GEE) will be used to analyze the effectiveness of the intervention at three-time points as compared with control group. The significance level will be set at  $P < 0.05$ , for a two-tailed test. SPSS 26.0 of IBM will be used to analyze collected data (SPSS Inc., Chicago, IL, USA). Multiple imputations would be used to replace missing data if data missing is inevitable.

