### **Phase 2: Pilot intervention study**

It involves the implementation of this study intervention based on the literature review, findings of phase one focus group interview and transformative learning theory (Dincer & Inangil, 2021; Tsimane & Downing, 2020). A feasibility study using a pilot randomized controlled trial design will assess the preliminary effect of the intervention on knowledge, attitude, empathy, and intention behavior of the fourth-year nursing students towards people with schizophrenia. The research outcome will be measured at three time points: Baseline (T0), after the intervention (T1), three months post-intervention (T2).

R software will be used to generate a randomization table in this study. To decrease the potential selection bias, allocation concealment will be applied to ensure there is no prior knowledge for group assignment (Suresh, 2011). A postgraduate student will be invited to help us generate the randomization table by R software. The participants' group belonging will be determined after the participants have signed the consent form.

The intervention programme will include investigative, collaborative, higher-order thinking, and interactive learning activities. For investigative learning activities, nursing students will be encouraged to access information through evidence-based research to discover the information by themselves and which will last about 6 hours.

The collaborative learning activities will include people recovered from schizophrenia to share their experiences throughout the treatment and recovery period with nursing students who will be encouraged to raise their questions. Nursing student will create scenario-based simulation and take roles in it. The contact activity will be held through online interviews. These collaborative learning activities will last about 4 hours.

The higher-order thinking activities will include nursing students' self-criticism after scenario-based simulation, nursing students will be asked to write their opinions about schizophrenia and people with schizophrenia. Nursing students will prepare concept maps for the problems a person with schizophrenia in daily life encounter and the corresponding solutions. The higher-order thinking activities are also held online and will last about 4 hours. Nursing students will interactively take part in the above-mentioned activities, which belong to interactive learning activities.

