### Preliminary Efficacy of the Intervention

We will assess the intervention efficacy at baseline, post intervention, and at three-month follow-up, including the participants' change in knowledge, attitude, intention behavior, and empathy. The self-assessment questionnaires will include as following:

1) Basic socio-demographic data will be gathered, and which will include information like age, gender, marital status, ethnic groups, university, province, religion, average family income per year, friends or family members with mental illness problems, mental illness history, whether they had contact with people with schizophrenia in the past, and whether they participated in any similar research before.

2) Knowledge about Schizophrenia Test (KAST)-Chinese version will be used to measure the stigma-related schizophrenia knowledge of participants. KAST, including 18 items, demonstrate an acceptable reliability coefficient of 0.68. The content validity index of items (I-CVI) ranged from 0.83 to 1.00, while the S-CVI/UA and S-CVI/Ave were 0.83 and 0.97, respectively, and known-group validity was satisfactory (Zhou et al., 2020).

3) Mental Illness Clinicians' Attitudes Scale (MICA)- Chinese version (Kassam, Glozier, Leese, Henderson, & Thornicroft, 2010; Li et al., 2014) will be used to measure stigma-related mental illness attitude of participants. MICA is a six-point scale that includes 16 items, and response options are from 1=totally agree to 6=totally disagree. The total score range is taken from 16-96. A lower score indicates participants having a positive attitude towards mental illness. The internal consistency is 0.72-0.75, and test-retest reliability is 0.76-0.87 of MICA in the Chinese version (Li et al., 2014; Pan Shengmao et al., 2013).

4) Reported and Intended Behavior Scale (RIBS)-Chinese version (Li et al., 2014) will be used to measure the stigma-related mental illness behavior of participants. RIBS is a five-point scale that includes eight items, and response options are designed as 1=totally disagree, 2=disagree, 3=do not know, 4=agree, 5=totally agree. The total score range is taken from 4-20 of items 5-8. The higher score

---

indicates the participants are more willing to contact people who have a mental illness. The internal consistency is 0.82, and test-retest reliability is 0.68 of RIBS in the Chinese version.

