5) Jefferson Scale of Empathy-Health Profession Students (JSE-HPS)-Chinese version (Hsiao et al., 2012) will be used to measure the nursing students' empathy towards people with schizophrenia. S-JSE-HPS is a seven-point scale that includes twenty items, and response options are designed as 1=totally disagree to 7= totally agree. The total score range is taken from 20-140. The higher score indicates the participants have greater empathic attitudes. The internal consistency is 0.93, and test-retest reliability is 0.92 of JSE-HPS in the Chinese version.

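### Adjusting the T1 and T2 comparisons for the T0 score already collected would give modestly more precise preliminary efficacy estimates than a GEE with T0 as an outcome time

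*Protocol*

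**What the plan says.** Under Phase 2: Pilot intervention study the Protocol fixes the schedule: "The research outcome will be measured at three time points: Baseline (T0), after the intervention (T1), three months post-intervention (T2"). Under Preliminary Efficacy of the Intervention it says "We will assess the intervention efficacy at baseline, post intervention, and at three-month follow-up", and describes the target as participants' "change in knowledge, attitude, intention behavior, and empathy". The Quantitative data analysis section then applies a GEE to "analyze the effectiveness of the intervention at three-time points as compared with control group". The only other use it gives for the T0 scale scores is descriptive: "The demographical variables and outcome variables were compared between groups at baseline". It names no baseline covariate for the T1 or T2 comparisons, and it does not write out the model terms or the working correlation.

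The same document gives retest figures for three of the four scales: "test-retest reliability is 0.68 of RIBS in the Chinese version", "test-retest reliability is 0.76-0.87 of MICA in the Chinese version" and "test-retest reliability is 0.92 of JSE-HPS in the Chinese version". For KAST it gives only a reliability coefficient of 0.68, not described as test-retest.

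**The concern.** The natural reading, supported by the reference to change, is a model with group, time and group by time over T0, T1 and T2. Its T1 and T2 effects are differences between arms in change from T0. A change score subtracts the whole baseline value, so it carries the full measurement noise of T0. Adjusting for T0 subtracts only the part that predicts follow-up, and is at least as precise for any correlation below 1, apart from a small cost for estimating the slope.

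The wording also allows a plain between-arm comparison at each time. That would make no use of T0 at T1 and T2 and would usually lose more.

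What is at stake is limited. The primary outcomes are feasibility and acceptability (Table 1), so only the preliminary efficacy estimates are affected. With 30 per arm, or about 24 after the planned drop-out, their intervals will be wide. The Implications for the future research section says the pilot should guide full-power trials, so any width that can be removed at no cost is worth removing.

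**Working it through.** **Inputs**

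- Sample size (Study Setting, Participants, Sampling and Sample size): 60 in total, 30 per arm, 20% drop-out. The stated 60 is reproduced as 48/(1 − 0.2) = 60, with 48 inside the quoted 24 to 50 range, and also as 50 × 1.2 = 60. Completers: 60 × 0.8 = 48, or 24 per arm.
- Correlation r between T0 and follow-up: not given. The Protocol's retest values serve as a proxy: 0.68 (RIBS), 0.76 to 0.87 (MICA), 0.92 (JSE-HPS). A value of 0.5 is added as an assumption, since correlation across an intervention and three months of follow-up may be lower than retest reliability. KAST has no usable figure.

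**Formulas** (score SD = 1, n per arm, same SD at each time)

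- Change from T0: variance = 2(1 − r) × 2/n
- Adjusted for T0: variance = (1 − r²) × 2/n
- Raw difference at follow-up: variance = 1 × 2/n
- Adjusted/change = (1 − r²)/[2(1 − r)] = (1 + r)/2
- Cost of estimating the T0 slope with 48 completers: about 1 + 1/(48 − 4) = 1.023
- 95% half-width = 1.96 × √variance

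Example, RIBS: change 2(1 − 0.68) = 0.64; adjusted 1 − 0.68² = 0.5376; ratio 0.5376/0.64 = 0.84; net of slope cost 0.84 × 1.023 = 0.859.

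**Results at 24 per arm**

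| Scale (r) | Adjusted/change, large sample | Net of slope cost | 24 per arm is worth | Half-width, change (SD) | Half-width, adjusted, net (SD) |
|---|---|---|---|---|---|
| Assumed (0.50) | 0.75 | 0.77 | 31.3 | 0.566 | 0.496 |
| RIBS (0.68) | 0.84 | 0.86 | 27.9 | 0.453 | 0.420 |
| MICA, low (0.76) | 0.88 | 0.90 | 26.7 | 0.392 | 0.372 |
| MICA, high (0.87) | 0.935 | 0.96 | 25.1 | 0.289 | 0.282 |
| JSE-HPS (0.92) | 0.96 | 0.98 | 24.5 | 0.226 | 0.224 |

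The fourth column is 24 divided by the unrounded net ratio. In standard-error terms the net reduction is about 12% at r = 0.5, 7% for RIBS, 5% to 2% for MICA and 1% for JSE-HPS. A simulation of 200,000 trials with 24 per arm, complete data and separate T0 slopes at T1 and T2 gave net ratios of 0.766, 0.859, 0.899, 0.956 and 0.981.

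**If a raw contrast at each time is meant.** Adjusted/raw = 1 − r²: 0.54 (RIBS), 0.42 to 0.24 (MICA), 0.15 (JSE-HPS).

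**Why T0 by time is needed.** Suppose r is 0.92 at T1 and 0.70 at T2, with 0.75 between T1 and T2 (all assumed). A single common slope averages to (0.92 + 0.70)/2 = 0.81.

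- T1: adjusted variance 1 − 2(0.81)(0.92) + 0.81² = 0.166, against 2(1 − 0.92) = 0.16 for change, so it is worse than the change score.
- With the slope cost included, simulation gives ratios of 1.065 at T1 and 0.88 at T2.
- Separate slopes give 0.98 and 0.87.

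**Why the working correlation matters if T0 stays a response.** Fitted GEEs (500 simulated trials, 24 per arm) gave these SDs of the T1 effect at r = 0.68 / 0.92:

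| Model | r = 0.68 | r = 0.92 |
|---|---|---|
| Group by time, T0 means free | 0.230 | 0.113 |
| T0 as covariate (common slope) | 0.213 | 0.111 |
| Common T0 mean, exchangeable | 0.213 | 0.110 |
| Common T0 mean, independence | 0.297 | 0.287 |

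The first row coincides with the change score, the last with the raw difference. Raw/change variance is 1/[2(1 − r)]: 1/0.64 = 1.56 at r = 0.68 and 1/0.16 = 6.25 at r = 0.92.

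**The case against.** The strongest counter-argument is scope. The planned analysis is not wrong. The Protocol gives one sentence on the GEE, and model terms, covariates and working correlation are normally left to a statistical analysis plan. A three-time GEE with a common T0 mean and exchangeable correlation also fits that sentence and would already take the gain. This stands as a limit: the group-by-time contrast is inferred, and an unseen plan may already adjust for T0. It does not remove the point, because the Protocol does make T0 an outcome time and gives the T0 scores no other role than a baseline comparison.

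The effect is also small and falls on non-primary outcomes, and the correlations are proxies. All of this is true. The uncertainty about r does not threaten the direction, however: a lower r makes the gain over the change score larger.

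The large raw-contrast ratios rest on the less likely reading, since the Protocol speaks of change, and should carry little weight. The figures assume 24 complete cases per arm and ignore the planned multiple imputation. Finally, the stated aim of refining a future trial under Phase 3 concerns the focus groups. The better support for caring about efficacy precision is the Implications section.

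**Conclusion.** The point holds as an optional improvement, not as an error. On the group-by-time reading, adjusting for T0 cuts the variance of the T1 and T2 effects by roughly 2% to 14%, net of slope estimation, at the Protocol's retest values, and by about 23% at an assumed correlation of 0.5. It is worth about four extra completers per arm for RIBS (24 to 27.9), one to three for MICA, and almost nothing for JSE-HPS if its correlation is really near 0.92. KAST cannot be sized from the document.

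This rests on the group-by-time reading, retest reliability as a stand-in for the correlation between T0 and follow-up, equal SDs over time, and 24 complete cases per arm. The sample size and the feasibility and acceptability outcomes are unaffected.

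**What to change.** In the Quantitative data analysis section, state that for each scale the group differences at T1 and T2 will be estimated from a GEE on the T1 and T2 scores, with group, time, group by time, the scale's own T0 score and T0 by time. The last term lets the T0 slope differ between the end of intervention and the three-month follow-up.

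If the team prefers to keep T0 as a response, it should constrain the arms to a common T0 mean and name a working correlation other than independence. An unstructured one lets the relation with T0 differ by time.

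The cost is a sentence or two of analysis wording. The T0 scores are already collected, the GEE procedure in the planned SPSS software still serves, and no visit, scale or participant is added.

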#### **Qualitative Content Analysis**

Manifest and latent content analysis will be adopted in this analysis. We will stop interview participants until data saturation is reached. NVivo 12 will be used to manage and organize qualitative data. There are five steps of the qualitative content analysis, which includes data preparing and organizing, reading and memoing, codes developing, generating categories, and representing the description and themes (Creswell, 2013).

#### **Issues of Trustworthiness of Data**

Qualitative validity requires the researcher use some procedures to examine the accuracy of the findings; while qualitative reliability requires the approach be consistent between different researchers and projects (Gibbs, 2018). Credibility, Dependability,

---

Transferability, and Confirmability are the four criteria in the trustworthiness of rigor qualitative studies (Lincoln & Guba, 1986). The quantitative data will be examined by two independent research assistants who will double-check the data collected to avoid data missing or inconsistency and ask the participants to reassure the data they provide if possible.

### **Implications for the future research**

This research is an open-label, small sample size pilot study. Guided by the theories of transformative learning and KAB theory. Intervention in decreasing schizophrenia stigma among nursing students through the online intervention will be more flexible for participants under the COVID-19 pandemic or other inconvenient face-to-face situations. Our result will also inform other population groups in mainland China about the education and contact intervention to decrease stigma of different kinds of mental disorders. Thus, we anticipate this study can guide future full power RCTs in decreasing different kinds of mental disorders stigma.

### **Research Schedule**

Time	Research implement process
July,2022-August,2022	First phase focus group interview
August 2022-October,2022	Second phase Pilot RCT intervention
October 2022-December,2022	Second phase process evaluation
January 2023-February,2022	Data analysis
March,2022-August,2023	Thesis writing

---

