### **Method**

#### **Study Design**

This study consists of quantitative and qualitative research design. There are three phases of the whole study.

- 1) In the first phase, a literature review and descriptive qualitative focus group interview will be used to inform the intervention development of a pilot RCT.
- 2) The second phase will be a pilot RCT. The pilot RCT consists of three stages,

---

including the investigative learning activity (6 hours), the collaborative learning activity (4 hours), and the higher-order thinking activity (4 hours). The control group has one stage—reading a book about schizophrenia knowledge.

3) The third phase is a process evaluation to explore the barriers or facilitators of the intervention in implementation, figure out additional problems which may affect the intervention in implementation, and refine the study design for a future full power RCT.

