### Appendix 1 Activities of schizophrenia education and contact intervention

Time	Intervention group activities		Control group activities
Week 1 -Week 4	
investigative learning: nursing students to access information through evidence-based research to discover the information themselves. A guide outline will be used to help nursing students to search information, and this outline may add some more guidance when stage one is done. Nursing students will be asked relevant information during week one, and every two points will require one hour. Students will be asked to spend two hours every two days to search relevant information of schizophrenia.
 
Collaborative learning activities Higher-order thinking activities interactive learning activities (Week 1-Week 4)
	
Week one: 1) Traditional Chinese culture and religion toward mental illness or schizophrenia. 2) Reasons of schizophrenia stigma formation. 3) Diagnosis and treatment of schizophrenia. 4) Violent, aggressiveness, and independence about schizophrenia. 5) How to communicate with people who have schizophrenia. 6) Daily stigma toward schizophrenia from media, like newspapers, TV series, movies, news, advertisement. 7) The early warning signs of schizophrenia and how to provide initial help to someone in a schizophrenia crisis and the symptoms, causes, and evidence-based treatments for schizophrenia. Summary: Knowledge and information sharing among students
 
Week two: Nursing students interview people who recover from schizophrenia share their experiences throughout the treatment and recovery period and discuss problems with them (a female and a male). Summary: Knowledge and information sharing among students
 
Week three: Scenario-based simulation, in the simulation application, students took the roles of the persons with schizophrenia or the nurses, and evaluate their performance, and view the events from a different perspective. Summary: Knowledge and information sharing among students
 
Week four: Nursing students' self-criticism after scenario-based simulation, nursing students will be asked to write their opinion about schizophrenia and People with Schizophrenia. After that, nursing students were read their opinions and discussed their assumptions. Self-reflection, critical reflection, and imaginative activities enabled them to examine themselves critically (Theme: What would I feel if I have schizophrenia). Nursing students prepared concept maps for the problems and solutions of a person with schizophrenia in the daily life.
	
Giving a book about schizophrenia to nursing students in the control group and asking them to finish reading it in a month.

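### Does the calendar need changing because the three-month follow-up has no row and can fall after the focus groups?

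*Protocol*

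**What the plan says.** Phase 2: Pilot intervention study sets the measurement times: "The research outcome will be measured at three time points: Baseline (T0), after the intervention (T1), three months post-intervention (T2". The Quantitative data analysis section uses all three in generalised estimating equations (GEE).

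Study Design numbers the process evaluation as the last of three phases: "The third phase is a process evaluation to explore the barriers or facilitators". The Phase 3 section gives its method and purpose: "This phase aims to collect feedbacks from online focus group interview", to learn what helped or hindered delivery. Appendix 1 lays the programme out over four weeks ("interactive learning activities (Week 1-Week 4").

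The Research Schedule is the only calendar. Its relevant rows are:

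- pilot intervention: "August 2022-October,2022"
- process evaluation: "October 2022-December,2022", labelled "Second phase process evaluation"
- data analysis: "January 2023-February,2022", where the closing year is evidently a misprint for 2023.

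No row is given to the three-month follow-up.

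**The concern.** T2 belongs to phase 2 and the process evaluation is phase 3, so a reader may expect T2 to be complete before the focus groups begin. The calendar does not deliver that for everyone. For some students the focus-group window closes before T2 is due, and their T2 lands in the period reserved for analysis.

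Two things could be at stake. First, the outcome scales are self-completed and the trial is open-label. Appendix 9 asks focus-group members how the programme affects the way they think about schizophrenia and whether the questionnaires suit their purpose. Such a conversation before T2 could move the T2 answers, probably in the intervention arm only, because the questions concern that arm's activities. Second, a model over three time points cannot be completed until the last T2 is in, and the schedule shows no time set aside for that.

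**Working it through.** **Inputs.** The intervention row is August to October 2022, the process-evaluation row is October to December 2022, and the analysis row is January to February 2023, reading the printed 2022 as a slip (all from Research Schedule). The programme lasts four weeks, or 28 days (Appendix 1). T2 is three months after the programme (Phase 2 section). The protocol prints no T2 date, so there is no stated figure to reproduce.

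**Formula.** Finish = start + 28 days; T2 = finish + 3 calendar months.

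| Start | Finish | T2 | Position |
|---|---|---|---|
| 1 Aug 2022 | 29 Aug | 29 Nov 2022 | inside focus-group window |
| 2 Sep | 30 Sep | 30 Dec 2022 | inside focus-group window |
| 3 Sep | 1 Oct | 1 Jan 2023 | after window, in analysis row |
| 3 Oct | 31 Oct | 31 Jan 2023 | after window, in analysis row |

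All 31 possible October finish dates give a T2 in January 2023. Students who finish by 30 September reach T2 by 30 December, so for them either order is possible.

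**Sensitivity to the meaning of three months.** Counting 84 days brings T2 for finishers on 1-8 October back into December. Counting 90 days does so for 1-2 October only, and 91 days for 1 October only. Most October finishers stay in January on every reading.

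**Room left for analysis.** January plus February 2023 is 31 + 28 = 59 days. After a last T2 on 31 January, 28 days remain.

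**Is an order actually laid down?** Study Design numbers the phases but does not say that each must end before the next begins. The Phase 2 section fixes T2 relative to the programme and does not mention focus groups. The Phase 3 section asks for feedback on implementation, which is available once the programme ends. Appendix 9 asks about questionnaires already completed, which fits baseline and post-programme forms alone just as well as all three. The schedule's own label calls the process evaluation second phase. That is either a numbering slip or a sign that it was meant to run alongside the follow-up. No passage requires T2 to come first.

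**Size of the possible bias.** It cannot be computed, because neither the number of early attendees nor the shift per attendee is given. What can be compared is exposure. The programme amounts to 6 + 4 + 4 = 14 hours (Study Design), and week four already has students write down, read out and discuss their opinions about schizophrenia (Appendix 1). A focus group lasts about 60 minutes (Data Collection) and covers similar ground.

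**The case for a change.** The strongest case for acting is that October finishers may be most of the sample. Phase 1 focus groups are scheduled through August 2022, and the intervention is to be built on their findings. If phase 1 uses its whole row, only programmes starting on 1 or 2 September could end by 30 September; every later start would finish in October. T2 is also the trial's only measurement beyond the end of the programme, and the Introduction criticises earlier studies for lacking follow-up. A follow-up that matters so much should have a place in the calendar, and asking for T2 before each focus group would need no extra staff or participants.

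Much of this stands. The dates are right, the share of students affected could be large, and the table does omit T2 and misnumber the phase. What does not follow is a need to reorder the work. Putting T2 first would hold the focus groups until at least three months after the programme. Members would then remember the sessions less well, which works against the stated purpose of learning about barriers and facilitators. It would also push transcription and qualitative analysis into the 28 days left for the GEE. That cost is set against a bias of unknown and probably small size, confined to scales the protocol treats as preliminary; Feasibility of Intervention makes feasibility and acceptability the main outcomes. Statisticians could reasonably choose either order.

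**Conclusion.** The concern describes the calendar correctly but does not call for a change. For October finishers T2 falls on 1-31 January 2023, after the focus-group window and within the analysis row. This rests on reading three months as calendar months and the analysis row as January to February 2023.

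Three things keep it from being a fault in the plan:

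- **No rule is broken.** The protocol never says that focus groups must follow T2. Collecting process feedback between the end of the programme and T2 is a fair trade-off between fresh recall and a possible small influence on later answers.
- **The analysis remains feasible.** With 60 participants, questionnaires collected online and 28 days left after the last possible T2, the GEE can be fitted once follow-up is complete. Any analyst would wait for that, because the model is specified over three time points. Baseline comparisons, recruitment counts and qualitative coding can begin in January without T2.
- **What remains is clerical.** The absent T2 row can be worked out from the protocol's own definition. The phase label is settled by Study Design and the Phase 3 section, which agree with each other. The table also carries obvious year misprints and reads as an outline by month.

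Following the protocol as written produces no demonstrable error in any result. An analyst who knows that some students attended a focus group before T2 can say so when interpreting the T2 scales.
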